2. OBJECTIVES, ENDPOINTS, AND HYPOTHESIS

2.1. Objectives and Endpoints

Primary

Objectives	Endpoints
Primary To assess safety and reactogenicity of the 3 vaccine regimens.	
 • Solicited local and systemic adverse events (AEs) for 7 days after each vaccination. • Unsolicited AEs from the time of informed consent form (ICF) signature until 28 days after the first vaccination, and thereafter, until 28 days after the second vaccination. • Serious adverse events (SAEs) throughout the study.

Secondary

Objectives	Endpoints
To assess immunogenicity of the 3 vaccine regimens.	T cell responses to the separate or combined protein peptide pools of HPV16 and HPV18 E2, E6 and E7 proteins, including specific CD4 ⁺ and CD8 ⁺ T cells producing IFN γ , tumor necrosis factor alpha (TNF α), or interleukin 2 (IL-2) (combined cytokine expression may also be assessed) will be determined by flow cytometry.

Exploratory

Objectives	Endpoints

To assess the frequency and kinetics of clearance of
 
 • persistent or recently diagnosed HPV16 and HPV18 infection (combined^a) and • persistent or recently diagnosed HPV16 infection and • persistent or recently diagnosed HPV18 infection 
of the 3 vaccine regimens compared to placebo over the study period.
	
Healthcare provider- and self-collected cervical samples obtained over the study period will be genotyped by a qualitative HPV genotyping test (Cobas[®], Roche) and a quantitative HPV PRC genotyping test to evaluate HPV16 and/or HPV18 viral clearance^b, defined as:
 
 • A negative HPV16 genotype over the study period after having a baseline HPV16 infection (persistent or recently diagnosed); OR • A negative HPV18 genotype over the study period after having a baseline HPV18 infection (persistent or recently diagnosed).
To assess regression of CIN1 and concomitant clearance of HPV16 and/or HPV18 infection of the 3 vaccine regimens compared to placebo over the study period.	
 • Regression of CIN1: A colposcopic impression of normal after having a baseline of CIN1, AND concomitant clearance of baseline (persistent or recently diagnosed) HPV16 and/or HPV18 infection (as defined above).

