9.1.2. Visit Windows

Participants should be encouraged to come on the exact day planned and use the visit window only if necessary. For the following visits, windows will be allowed as indicated:

- Second vaccination: \pm 7 days

^a Depending on the time of the occurrence, any participant who receives a prohibited concomitant medication will not be included in the immunogenicity analyses.

- 7 days post-vaccination safety only visit: \pm 2 days
- 21 days post-Dose 2 vaccination safety, immunogenicity and virology visit: \pm 3 days
- 28 days post-vaccination safety only visit (telephone call): \pm 3 days
- 2 months post-Dose 2 vaccination safety and virology visit: \pm 5 days
- 6 months post-Dose 1 safety and virology visit: \pm 14 days
- 6 months post-Dose 2 vaccination safety, immunogenicity and virology visit: \pm 14 days
- 12 months post-Dose 1 safety, immunogenicity and virology visit: \pm 14 days

If a participant cannot be vaccinated within the allowed window, then that vaccination should not be administered. However, vaccination outside of the window (in particular if the window is missed due to a study pause) can be assessed on a case-by-case basis upon discussion between investigator and sponsor.

No visit windows are applicable for telephone calls to sentinel participants at 1 day post vaccination.

The timings of the second vaccination and of Visit 12 will be determined relative to the actual day of the first vaccination. The timing of visits 7, 8, 9, 10, 11 and 13 will be determined relative to the actual day of the second vaccination.

9.1.3. Screening Period (Days -42 to -2): Visit 1

Only participants complying with the inclusion and exclusion criteria specified in Section 4.1 and Section 4.2, respectively, will be included into the study. The investigator will provide detailed information on the study to the participants and will obtain written informed consent prior to each participant's participation in the study. All the procedures described in the [Time and Events Schedule](#) will only take place after written informed consent has been signed.

The following evaluations will be performed on participants to determine overall eligibility:

- Review of inclusion/exclusion criteria
- Demographic information
- Medical history and pre-study medications
- Physical examination including vital signs measurement (supine systolic and diastolic blood pressure, heart rate and oral temperature) and height and weight

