An abbreviated physical examination (at the discretion of the investigator), measurement of vital signs, urine pregnancy test (for women of childbearing potential), self-collected cervico-vaginal sample for type-specific HPV16 and HPV18 PCR and pre-vaccination symptoms check will be performed for all participants pre-vaccination. Pre-dose samples for immunogenicity assessments will be collected. Before vaccination, the investigator must check for any symptoms of an acute illness or oral temperature ≥ 38.0 °C. If the vaccination visit cannot be rescheduled within the allowed window or the contraindications to vaccination persist, the sponsor should be contacted for further guidance.

Administration of second dose of study vaccine.

After vaccination, participants will remain under observation at the study site for at least 30 minutes for presence of any acute reactions and solicited events. Any unsolicited, solicited local or systemic AEs and vital signs will be documented in the eCRF by study-site personnel following this observation period.

Participants will be provided with a participant diary, thermometer, and ruler to measure and record oral body temperature, solicited local and systemic AEs for 7 days post-vaccination.

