9.1.4.3. Post-second Vaccination Follow-Up

- **1 Day Post-second Vaccination (sentinel participants only): Visit 7**

This visit will be a telephone call to check participant diaries and to collect safety information (solicited and unsolicited AEs, SAEs and concomitant medications).

- **7 Days Post-second Vaccination: Visit 8**

This visit will include an abbreviated physical examination (at the discretion of the investigator), vital signs measurement, and recording of any AEs/SAEs and concomitant medications. Samples for safety laboratory testing (hematology and biochemistry) will be collected. The participant diary will be collected and reviewed.

- **21 Days Post-second Vaccination: Visit 9**

This visit will include an abbreviated physical examination (at the discretion of the investigator), vital signs measurement, self-collected cervico-vaginal sample for type-specific

HPV16 and HPV18 PCR and recording of any AEs/SAEs and concomitant medications. Samples for immunogenicity assessments will be collected.

- **28 Days Post-second Vaccination: Visit 10**

This visit will be a telephone call to collect safety information (unsolicited AEs, SAEs and concomitant medications).

- **2 Months Post-second Vaccination: Visit 11**

This visit will include an abbreviated physical examination (at the discretion of the investigator), vital signs measurement, a self-collected cervico-vaginal sample for type-specific HPV16 and HPV18 PCR and recording of any SAEs and concomitant medications (related to SAEs only).

- **6 Months Post-second Vaccination: Visit 13**

This visit will include an abbreviated physical examination (at the discretion of the investigator), vital signs measurement, self-collected cervico-vaginal sample for type-specific HPV16 and HPV18 PCR and recording of any SAEs and concomitant medications (related to SAEs only).

Samples for immunogenicity assessments will be collected.

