12.3. Procedures

12.3.1. All Adverse Events

Unsolicited AEs and special reporting situations will be reported from the time of ICF signature until 28 days after the first vaccination, and thereafter, for 28 days after each subsequent dose of study vaccine. Unsolicited AEs with the onset date outside the time frame defined above (>28 days after previous study vaccination) that are ongoing on the day of the subsequent vaccination should be recorded on the eCRF AE page.

Solicited AEs will be recorded by each participant in the participant diary for 7 days after each dosing. The investigator will review each participant's diary at the subsequent in-clinic visit; diary information will be transcribed by the study personnel in the on-site assessment forms in the eCRF.

All SAEs and AEs leading to discontinuation from the study vaccination (regardless of the causal relationship) are to be reported for the duration of the study. The sponsor will evaluate any safety information that is spontaneously reported by an investigator beyond the time frame specified in the protocol.

All AEs, regardless of seriousness, severity, or presumed relationship to study vaccine, must be recorded using medical terminology in the source document and the eCRF. Whenever possible, diagnoses should be given when signs and symptoms are due to a common etiology (eg, cough, runny nose, sneezing, sore throat, and head congestion should be reported as "upper respiratory infection"). Investigators must record in the eCRF their opinion regarding the relationship of the AE to study vaccine. All measures required for AE management must be recorded in the source document and reported according to sponsor instructions.

The sponsor assumes responsibility for appropriate reporting of AEs to the regulatory authorities. The sponsor will also report to the investigator (and the head of the investigational institute where required) all SUSARs. The investigator (or sponsor where required) must report SUSARs to the appropriate IEC/IRB that approved the protocol unless otherwise required and documented by the IEC/IRB. A SUSAR will be reported to regulatory authorities unblinded. Participating investigators and IEC/IRB will receive a blinded SUSAR summary, unless otherwise specified.

Participants will be provided with a "wallet (study) card" and instructed to carry this card with them for the duration of the study indicating the following:

- Study number

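### The two 28-day safety calls may be made at 25 days, before the unsolicited-AE period of the primary endpoint ends, and after Dose 2 no later scheduled visit asks about non-serious events

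*Protocol*

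**What the plan says.** Section 2.1 of the protocol makes unsolicited AEs one of three primary endpoint components, collected from consent "signature until 28 days after the first vaccination, and thereafter, until 28 days after the second vaccination".

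Each period closes with a telephone contact, Visit 5 after Dose 1 and Visit 10 after Dose 2. Section 9.1.2 lists it as "28 days post-vaccination safety only visit (telephone call") with ±3 days. The Time and Events Schedule agrees, with Day 29±3 and Day 85±3. Section 9.1.4.3 describes Visit 10 as follows: "This visit will be a telephone call to collect safety information (unsolicited AEs, SAEs and concomitant medications"). Section 9.1.4.2 gives Visit 5 the same content.

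The next contact after Visit 10 is Visit 11 (Day 113±5). Its safety content in Section 9.1.4.3 is "recording of any SAEs and concomitant medications (related to SAEs only"). Visits 12, 13 and 14 carry the same restriction.

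The next contact after Visit 5 is Visit 6, the second vaccination (Day 57±7). It includes a pre-vaccination symptoms check, and Section 9.1.4.1 adds: "Any unsolicited, solicited local or systemic AEs and vital signs will be documented in the eCRF by study-site personnel following this observation period". Section 12.3.1 further says that unsolicited AEs with onset more than 28 days after the previous vaccination "that are ongoing on the day of the subsequent vaccination should be recorded on the eCRF AE page".

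**The concern.** The endpoint is defined over 28 days, but the protocol lets the question that closes the period be put before the period is over. Section 12 names open verbal questioning as the preferred way of detecting AEs. The diary does not fill the gap: it covers solicited symptoms for 7 days only. If the call is early and nobody asks again, a non-serious event in the last days reaches the database only when the woman raises it herself.

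Section 11.4 summarises the percentage of participants with an AE having onset within 28 days of a vaccination. What is at stake is how completely the tail of that period is ascertained, in a first-in-human trial whose primary objective is safety. An analysis rule cannot repair this later, because it cannot recover events that were never elicited.

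**Working it through.** **Inputs.** Dose 1 on Day 1 and Dose 2 on target Day 57. Closing calls on Day 29±3 and Day 85±3, Visit 6 on Day 57±7, Visit 9 on Day 78±3 and Visit 11 on Day 113±5 (Time and Events Schedule). The ±3 also stands in Section 9.1.2. Visits 9, 10 and 11 are timed from the actual second vaccination, so the Dose 2 intervals below do not depend on when that dose is given.

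**Reproducing the schedule.** 1 + 28 = Day 29 and 57 + 28 = Day 85. Both match, and the two places agree on ±3. There is no inconsistency between the window list and the schedule.

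**Earliest compliant call.**
- Visit 5: 29 − 3 = Day 26, and 26 − 1 = 25 days after Dose 1.
- Visit 10: 85 − 3 = Day 82, and 82 − 57 = 25 days after Dose 2.

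**Days not yet elapsed at that call.** 28 − 25 = 3 days (post-dose days 26, 27 and 28). 3/28 = 10.7% of the period. This is the maximum for one woman after one dose.

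**Who asks next.**

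| After | Next contact | Gap from the earliest call | Non-serious AEs on the visit's list? |
|---|---|---|---|
| Visit 5 (Day 26) | Visit 6, Day 50 to 64 | 50 − 26 = 24 to 64 − 26 = 38 days | Partly: symptoms check before the dose, unsolicited AEs documented after it; no stated look-back to days 26 to 28 |
| Visit 10 (Day 82) | Visit 11, Day 108 to 118 | 108 − 82 = 26 to 118 − 82 = 36 days | No: serious events only, as at Visits 12 to 14 |

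Visit 9 does record AEs in person, but it falls at 21±3 days after Dose 2, at the latest day 24, and so cannot reach days 26 to 28. The early exit visit records any AEs, but only for women who leave the study.

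**After the change.** With a window of 0 to +3 days the earliest call is on post-dose day 28, and 28 − 28 = 0 days fall after it. The latest calls stay at Day 32 and Day 88, well before the earliest Visit 6 (Day 50) and the earliest Visit 11 (Day 108).

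**The case against.** The strongest reply is that the call does not end the reporting period. The protocol fixes that period by calendar in Sections 2.1, 9.2.1, 12.1.1 and 12.3.1, and the Time and Events Schedule shows unsolicited-AE recording as continuous. An event starting on day 27 remains reportable whenever the site learns of it. This stands. A reader might infer that women called early contribute a shorter follow-up period, or that the reported percentages are understated by about a tenth. The documents support neither. What may be missing is one prompt, and 3 of 28 days is a ceiling for an individual woman, not an estimate of lost events.

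Second, the Dose 1 side is largely covered. Visit 6 brings the woman to the site, and Section 12.3.1 requires AEs from beyond day 28 to be recorded if ongoing at that vaccination. Section 11.4 foresees summaries of AEs reported before a subsequent dose. A site doing this is unlikely to pass over events from days 26 to 28. This mostly stands. What remains after Dose 1 is a non-serious event that has resolved by Visit 6 and goes unmentioned.

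Third, Section 9.1.2 tells sites to keep the exact day and use the window only when needed. One should therefore not assume calls spread evenly over the seven permitted days and derive an average loss from that. The documents give no distribution of call days.

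Fourth, a reader might infer that the pausing rule on two Grade 3 unsolicited AEs of the same type is weakened. The link is too thin to carry weight. Related AEs of Grade 3 or above must be notified within 24 hours of the site's awareness (Section 11.9), serious events are captured throughout the study, and participants carry a card with a 24-hour investigator number.

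None of this supplies a scheduled question about non-serious events on days 26 to 28 when Visit 10 is made early.

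**Conclusion.** The point holds as a minor weakness in design. A call 25 days after the dose complies with the protocol, and after Dose 2 no later scheduled visit asks about non-serious AEs. Events with onset on post-dose days 26 to 28 then depend on the woman volunteering them. The exposure is at most 3 of 28 days (10.7%) for a woman called at the earliest time, and none for a woman called on day 28 or later. After Dose 1 the gap is smaller for the reasons given above.

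The likely effect is slight under-ascertainment of late, non-serious events. The same window applies to vaccine and placebo, so it gives no ground for a claim of bias between arms. Safety is analysed descriptively, and no planned conclusion turns on these days. The sizes rest only on the protocol's visit days. How many calls would in fact be early cannot be derived from the document.

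**What to change.** Preferred: in Section 9.1.2 and the Time and Events Schedule, make the windows for Visits 5 and 10 one-sided, 0 to +3 days (Day 29 to 32, and Day 85 to 88 when Dose 2 is on Day 57). Every completed call then covers the whole 28-day period.

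Alternative: keep ±3 and add to Visit 11, and for symmetry to Visit 6, an instruction that when the 28-day call was made early, the site asks about and records unsolicited AEs with onset through day 28 after the dose. This is the weaker option. Visit 11 lies 51 to 61 days after Dose 2, so the woman would be recalling minor events from 51 − 28 = 23 to 61 − 26 = 35 days earlier.

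Either change is a line or two of text and adds no visit or procedure. The cost of the first is that the permitted span for a telephone call shrinks from seven days to four.

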9.1.4. Vaccination and Follow-up Period (Day 1 to Day 366)

9.1.4.1. Vaccination (Day 1, and Day 57)

- **Day 1/Day of Randomization/Vaccination 1: Visit 2**

After an abbreviated physical examination (at the discretion of the investigator), measurement of vital signs, urine pregnancy test (for women of childbearing potential), self-collected cervico-vaginal sample for type-specific HPV16 and HPV18 PCR, HSV-2 serology test, and pre-vaccination symptoms check, eligible participants will be randomized as described in Section 5. If a participant's clinical status changes (including any available laboratory results or receipt of additional medical records) after screening but before the first dose of study vaccination is given such that she no longer meets all eligibility criteria, then the screening laboratory tests should be repeated and the Day 1 visit rescheduled, or the participant should be excluded from participation in the study. Pre-dose samples for baseline immunogenicity assessments will be collected. Before vaccination, the investigator must check for any symptoms of an acute illness or oral temperature ≥ 38.0 °C. If the vaccination visit cannot be rescheduled within the allowed window or the contraindications to vaccination persist, the sponsor should be contacted for further guidance.

Administration of first dose of study vaccine.

After vaccination, participants will remain under observation at the study site for at least 30 minutes for presence of any acute reactions and solicited events and will be allowed to leave the vaccination site at approximately 45 minutes post-vaccination. Any unsolicited, solicited local or systemic AEs and vital signs will be documented in the eCRF by study-site personnel following this observation period.

Participants will be provided with a participant diary, thermometer, and ruler to measure and record oral body temperature, solicited local and systemic AEs for 7 days post-vaccination.

Unsolicited AEs will be recorded on the AE page of the eCRF from the time of ICF signature until 28 days after the first vaccination, together with information about any concomitant medications. SAEs will be collected until the study end (Day 366).

- **Day 57/Vaccination 2: Visit 6**

An abbreviated physical examination (at the discretion of the investigator), measurement of vital signs, urine pregnancy test (for women of childbearing potential), self-collected cervico-vaginal sample for type-specific HPV16 and HPV18 PCR and pre-vaccination symptoms check will be performed for all participants pre-vaccination. Pre-dose samples for immunogenicity assessments will be collected. Before vaccination, the investigator must check for any symptoms of an acute illness or oral temperature ≥ 38.0 °C. If the vaccination visit cannot be rescheduled within the allowed window or the contraindications to vaccination persist, the sponsor should be contacted for further guidance.

Administration of second dose of study vaccine.

After vaccination, participants will remain under observation at the study site for at least 30 minutes for presence of any acute reactions and solicited events. Any unsolicited, solicited local or systemic AEs and vital signs will be documented in the eCRF by study-site personnel following this observation period.

Participants will be provided with a participant diary, thermometer, and ruler to measure and record oral body temperature, solicited local and systemic AEs for 7 days post-vaccination.

9.1.4.2. Post-first Vaccination Follow-Up

The randomization, vaccination process and safety evaluations described below for HPV16 infected participants will be performed in the same manner and independently among HPV18 infected participants.

- **1 Day Post-first Vaccination: Sentinel Participants: Visit 3**

At 1 day after the first vaccination, a telephone call will be made to the 5 sentinel participants (2 in Step 1 and 3 in Step 3); vaccination of additional participants will be halted until a 24-hour and 7-day post vaccination blinded safety review of solicited and unsolicited AEs are performed by the PI and the SRP.

- **7 Days Post-first Vaccination: Visit 4**

This visit will include an abbreviated physical examination (at the discretion of the investigator), vital signs measurement, and recording of any AEs/SAEs and concomitant medications. Samples for safety laboratory testing (hematology and biochemistry) will be collected. The participant diary will be collected and reviewed.

- **28 Days Post-first Vaccination: Visit 5**

This visit will be a telephone call to collect safety information (unsolicited AEs, SAEs and concomitant medications).

- **6 Months Post-first Vaccination (Week 26): Visit 12**

This visit will include an abbreviated physical examination (at the discretion of the investigator), vital signs measurement, self-collected cervico-vaginal sample for type-specific

HPV16 and HPV18 PCR and recording of any SAEs and concomitant medications (related to SAEs only).

- **12 Months Post-first Vaccination (Week 52): Visit 14**

This visit will include an abbreviated physical examination (at the discretion of the investigator), vital signs measurement, healthcare provider-collected cervical sample for type-specific HPV16 and HPV18 PCR, self-collected cervico-vaginal sample for type-specific HPV16 and HPV18 PCR and recording of any SAEs and concomitant medications (related to SAEs only). At this visit all participants will undergo a colposcopic evaluation and an HSV-2 serology test. Samples will be shipped and tested in a central sponsor designated laboratory. Samples for immunogenicity assessments will be collected.

